### **3. STUDY AIMS/STUDY OBJECTIVES**

The goal of this research is to assess the technical feasibility of simultaneous breast DCE MRI with  $^{18}\text{F}$ -FES PET for measuring ER in patients with DCIS and identifying patients with low-risk of disease recurrence. We hypothesize that quantitative  $^{18}\text{F}$ -FES uptake parameters from PET/MRI will correlate well with the ER immunohistochemistry score and with low-risk recurrence scores.

#### **3.1 Primary objective:**

To measure  $^{18}\text{F}$ -FES uptake of biopsy-proven DCIS using breast PET/MRI. The reference standard will be ER expression measured with immunohistochemistry.

### **3.2 Secondary objectives:**

- Determine the optimal cut-point  $^{18}\text{F}$ -FES uptake value for distinguishing between ER+ and ER-negative DCIS.
- Determine the test-retest reproducibility of quantitative assessment of tumor  $^{18}\text{F}$ -FES uptake.
- Determine the optimal cut-point  $^{18}\text{F}$ -FES uptake value for distinguishing between low-risk DCIS and intermediate/high-risk DCIS.
- Estimate the association of quantitative  $^{18}\text{F}$ -FES uptake (continuous  $\text{SUV}_{\text{max}}$ ) with research-based Oncotype DX DCIS scores (0-100)
- Measure the upgrade rate to invasive cancer at surgical excision.
- To correlate tumor  $^{18}\text{F}$ -FES uptake with serum estradiol and sex hormone binding globulin levels.

### **3.3 Exploratory objective:**

To correlate tumor cell density with  $^{18}\text{F}$ -FES uptake on PET/MRI.

**Study duration:** 3 years. Our estimated rate of accrual is approximately 1 participant every 1-2 months.

## **4. SELECTION OF PATIENTS**

### **Study Population:**

Female patients of all races and ethnic backgrounds at least 18 years of age with a current diagnosis of DCIS who are undergoing breast MRI for staging and extent of disease ordered by their provider as part of routine clinical care.

### **4.1 Eligibility Criteria**

#### **Inclusion Criteria:**

- 4.1.1 Women 18 years of age or older
- 4.1.2 Diagnosis of biopsy-proven DCIS without invasion or microinvasion measuring at least 1.0 cm in diameter by any imaging modality
- 4.1.3 Undergoing diagnostic breast MRI ordered by the referring clinician for staging and extent of disease†

#### **Exclusion Criteria:**

- 4.1.4 Inability or unwillingness to provide informed consent to the study

---

† Patients with newly diagnosed DCIS from a screening breast MRI are also eligible to participate in this study. For these subjects, the research breast PET/MRI should be performed prior to any treatment or surgery for DCIS.

- 4.1.5 Surgery, radiation, neoadjuvant chemo/endocrine therapy for the current malignancy prior to study enrollment
- 4.1.6 Patients currently taking or have taken an ER-blocking medication (e.g. tamoxifen, raloxifene) within 6 weeks prior to study enrollment
- 4.1.7 Pregnant or lactating women
- 4.1.8 Patient with intolerance or contraindications for MRI or gadolinium-based contrast agents
- 4.1.9 Patient girth exceeds the bore of the MRI/PET scanner
- 4.1.10 Patients with a history of allergic reaction attributable to compounds of similar chemical or biologic composition to FES
- 4.1.11 Patients in liver failure as judged by the patient's physician, due to the hepatobiliary clearance of F-FES
- 4.1.12 Patients requiring intravenous (IV) conscious sedation for imaging are not eligible; patients requiring mild, oral anxiolytics for the clinical MRI scan will be allowed to participate as long as the following criteria are met:
  - 4.1.12.1 The patient has their own prescription for the medication
  - 4.1.12.2 The informed consent process is conducted prior to the self-administration of the medication.
  - 4.1.12.3 The patient comes to the research visit with a driver or an alternative plan for transportation (e.g. Uber, taxi, etc.).

## 5. RESEARCH DESIGN AND METHODS

### 5.1 Study Design

This prospective, single-arm, observational, single-institutional research study will enroll women with DCIS scheduled for diagnostic breast MRI for preoperative staging/extent of disease evaluation. The proposed work-flow is described in the schema above. Eligible patients will be consented for participation in the research study which will involve the simultaneous acquisition of F-FES PET imaging data during a standard dynamic contrast enhanced clinical breast MRI performed prior to surgical excision. Patients with ER+ DCIS will be offered to participate in an optional sub-study which will involve a second (test-retest) F-FES PET/MRI examination until we have accrued up to 5 patients. The results of the F-FES PET imaging component of the examination will not be used to guide patient management. However, the clinical breast MRI component of the examination will be interpreted and reported with management recommendation as per routine clinical care. Surgical management, radiation therapy, and adjuvant therapy will follow standard of care. A research-based Oncotype DX DCIS score will be obtained from the surgical specimen for research purposes only since this test is currently not frequently used clinically at our institution (only about 1-5% DCIS patients locally).

Patients with DCIS may also participate in this study if a clinical breast MRI has already been performed. In this scenario, a research F-FES breast PET/MRI will be performed on a separate day as the clinical breast MRI exam prior to surgery.

The primary objective is to measure F-FES uptake of biopsy-proven DCIS using PET/MRI. The reference standard will be ER expression measured with immunohistochemistry. Secondary objectives include 1) to determine the optimal cut-point F-FES uptake value for distinguishing between ER+ and ER-negative DCIS; 2) to determine the test-retest reproducibility of quantitative assessment of tumor F-FES uptake; 3) to determine the optimal cut-point F-FES uptake value for distinguishing between low-risk DCIS and intermediate/high-risk DCIS; 4) to estimate the association of quantitative F-FES uptake (continuous SUVmax) with research-based Oncotype DX DCIS scores (0-100); 5) to measure the upgrade rate to invasive cancer at surgical excision; 6) to correlate tumor F-FES uptake with serum estradiol and sex hormone binding globulin levels. An exploratory objective is to correlate tumor cell density with F-FES uptake on PET/MRI.

## 5.2 Reference Standard for ER Expression

The primary objective is to measure F-FES uptake of biopsy-proven DCIS using PET/MRI. The reference standard will be ER expression measured with immunohistochemistry performed as per the current standard of care.

ER status is reported as positive or negative and includes a percentage of cells staining positive as well as intensity of staining. This information will be obtained from the clinical pathology report in the subjects' electronic medical record and will be used to calculate a semi-quantitative Allred score (44). If the information needed to calculate the Allred score is not included in the clinical pathology report, a pathologist on the research study team will review the existing ER IHC slides.

The Allred score is the sum of the proportion score and the intensity score (**Table 1**) (44). ER-negative cancers can have either an Allred score of 0 or 2 (1+1). ER-positive cancers can have an Allred score of 3, 4, 5, 6, 7, or 8. An Allred score of 1 does not exist.

**Table 1: Allred Scoring System**

Percentage of Positive-Staining Tumor Cells	Proportion Score (PS)	Average Intensity of Positive Tumor Cells	Intensity Score (IS)
None	0	None	0
<1%	1	Weak	1
1-10%	2	Intermediate	2
10-33%	3	Strong	3
33-66%	4		
66-100%	5		

## 5.3 Study Calendar/Schedule

The study calendar/schedule is detailed in **Table 2**.

**Table 2: Study Calendar/Schedule**

Study Activity	Baseline a	Imaging Day b	Clinical Follow-Up c
Informed Consent h	X		
Demographics d	X		
Medical History d	X		
Radiology Reports d	X		X
Pathology Reports (Breast biopsy and final surgical excision) d	X		X
Concomitant Medication Review		X	
Pregnancy Screening		X	
Day of last menstrual period (if premenopausal)		X	
Height and Weight		X	
Blood for Hormone Levels		X g	
 F-FES PET/MRI i		X	
Adverse Event Evaluation e		X	X
Research-based Oncotype DX DCIS Score f			X

- (a) Baseline is defined as the time period from initial subject contact until injection of F-FES.
- (b) Imaging Day is defined as the day of the research F-FES PET/MRI imaging session.
- (c) Subjects' medical records are followed until final surgical excision and clinical determination of adjuvant therapy plan. Any standard of care labs, procedures, and/or imaging exams obtained during this time period will be reviewed. Data regarding recommended adjuvant therapy (radiation and endocrine therapy) will be recorded. There are no protocol requirements during this time frame.
- (d) Clinical data, including age, race/ethnicity, primary breast cancer data (standard clinical histopathology including tumor biomarkers, location, size, and date of biopsy/diagnosis), mammographic breast density, and menopausal status will be recorded from the electronic medical record.
- (e) Adverse events occurring within one day after F-FES infusion will be recorded by the study coordinator who will contact the subject within 1 to 3 days.
- (f) Oncotype DX DCIS score will be obtained from the electronic medical record if performed clinically (only 1-5% of DCIS patients locally expected) and will also be performed as a separate research-based assay using the resection specimen.
- (g) Blood sample collected will be up to 10 mLs total.
- (h) During the COVID-19 pandemic, consent procedures will be conducted by phone, when possible, to minimize face-to-face contact subjects have with the research team. An encrypted copy of the consent form will be mailed or emailed to subjects prior to the scheduled consent phone call.
- (i) Subjects who are unable to undergo a PET/MRI scan will be invited to undergo a PET/CT along with a separate MRI scan

#### 5.4 Clinical Breast MRI (Standard of Care)

The clinical breast MRI will be performed and interpreted according to standard clinical practice. If additional management recommendations are generated based on the clinical breast MRI (i.e. identification of unsuspected suspicious findings requiring biopsy), the research examinations will ideally be scheduled prior to the date of scheduled intervention(s) but can also be performed after a biopsy

procedure. The patient will be informed of this possibility at the time of initial consent.

## 5.5 Research Breast $^{18}\text{F}$ -FES PET/MRI

### 5.5.1 Timing of $^{18}\text{F}$ -FES PET/MRI

Patients must complete the research breast PET/MRI study prior to surgical/oncologic intervention for their biopsy-proven breast cancer as part of their routine clinical care. Ideally, the research breast PET/MRI study should be performed prior to any interventions (i.e. biopsies) prompted by the clinical breast MRI if performed prior to the research study, but this is not required. If patients are also scheduled for clinical nuclear medicine studies using  $^{99\text{m}}\text{Tc}$ -based or  $^{18}\text{F}$ -based radiopharmaceuticals, the research study should be scheduled on a separate day.

### 5.5.2 Patient Preparation

The patient does not need to be fasting for  $^{18}\text{F}$ -FES PET/MRI. Prior to arrival, the patient should be well-hydrated (encourage drinking two-three 8-12 oz glasses of water) unless a fluid-restriction diet is prescribed by the patient's treating physician (e.g., congestive heart failure). The patient should continue to take any of their prescribed medications as scheduled by their treating physician.

Upon arrival, subject compliance with pre-procedure instructions will be confirmed. Subject completion of the informed consent documentation will also be confirmed. The patient's height and weight will be measured and recorded. Women with childbearing potential will be asked to confirm they are not pregnant. If they cannot confirm, they will have a urine pregnancy test either at the imaging study visit or within 7 days prior to the imaging study visit.

### 5.5.3 $^{18}\text{F}$ -FES Administration

The patient will have an intravenous line placed, typically in the hand or arm opposite to the known primary breast cancer,  $^{18}\text{F}$ -FES will be given by 2-minute infusion, and the dose administered will be approximately 6 mCi  $\pm$  20%. The injection site will be inspected by the technologist to assess for any possible infiltration. The patient will wait approximately 60 minutes to allow for biodistribution and tumor uptake of the radiopharmaceutical prior to imaging. The patient should void prior to image acquisition.

All adverse events occurring within a 24-hour period post-infusion will be recorded (a phone call to the participant performed 1 to 3 days after  $^{18}\text{F}$ -FES infusion is acceptable means of collecting this information). The adverse events to be specifically monitored during the infusion include localized discomfort at the IV injection site, pain, respiratory difficulties, flushing, dizziness, pruritus/rash, and any other symptoms that could be

secondary to an anaphylactic reaction. The subject will be instructed to report any subjective symptoms or sensory changes noted.

**5.5.4 Imaging Quality Assurance (QA)/Quality Control (QC) Procedure**  
QA/QC procedures will include review of DICOM files against study protocols. The PET/MRI scanner must be kept calibrated in accordance with the manufacturer's recommendations. The scanner should routinely be assessed for quantitative integrity and stability by being tested using various imaging protocols on a standard phantom. For SUV measurements, this assessment should include a comparison against a dose calibrator to ensure accuracy; that is, a comparison of the absolute activity measured versus the measured activity injected, should be performed.

A daily QC check must be performed at the beginning of the day, including PET/MRI scanner and dose calibrator, in accordance with the manufacturer recommendations. If any of the QC results are outside of the manufacturer's guidelines, the study must be rescheduled and the problem rectified before scanning any patients.

**5.5.5  $^{18}\text{F}$ -FES PET/MRI Imaging Acquisition**

Image acquisition and reconstruction protocols specific to this research study will be available in a separate "Imaging Manual". The protocol is briefly described here.

The patient will be escorted to the GE Discovery 750W 3T MR scanner containing the PET insert and an 8-Channel breast coil qualified for PET/MRI located in the basement level of WIMR Tower 1. Directed breast PET/MRI data will be acquired with the patient in the prone position. Imaging will be performed by research technologists under guidance of the principal and/or collaborating investigators. MRI-sequences utilized in a standard clinical breast MRI will be obtained, including T2-weighted fat suppressed and diffusion weighted imaging (DWI) prior to gadolinium contrast administration followed by T1-weighted fat suppressed DCE imaging. The MRI sequences will include standard clinical sequences and may include research MRI sequences under development and evaluation at the University of Wisconsin. A standard MR-based attenuation correction algorithm provided by GE will also be used for this study. Breast specific PET emission data will be acquired simultaneous with the MR images. The entire examination is expected to take 30 – 40 minutes. Post-processing includes PET image reconstruction, correction for attenuation, scatter, and motion, and co-registration with the MR images.

In the rare instance that the subject is unable to be imaged using the simultaneous PET/MRI scanner (e.g. excessive girth, technical issue with scanner performance), the subject will undergo two separate scans. A breast MRI (approximately 30 to 40 minutes) will be performed using a 3T

breast MRI scanner (e.g. GE Signa Premier) using MRI sequences as described above, and a breast specific PET/CT scan will be performed using a PET/CT scanner (e.g. Discovery IQ or GE Discovery 710) located in the Department of Radiology in the Wisconsin Institutes for Medical Research (WIMR) Tower 1. The subject will be positioned prone with arms overhead. Following a CT scout (topogram), a directed low-dose, non-contrast, non-breathhold, non-diagnostic CT scan through the chest/breasts will be performed for attenuation correction calculations. Next, a static PET emission scan of the thoracic region to specifically cover the breasts will be acquired in 3D acquisition mode. The entire examination is expected to take approximately 15-20 minutes. Post-processing includes PET image reconstruction, correction for attenuation and co-registration with the CT images and also with the separately obtained breast MRI.

#### 5.5.6 $^{18}\text{F}$ -FES PET/MRI Image Analysis

Images will be reviewed for general quality. The known biopsy-proven breast cancer(s) will be identified on the MRI/PET examination based on its known location from the prior clinical breast MRI, if performed, or the patient's previous imaging, as is typically done in routine clinical practice. MRI images will be used to localize the lesion(s), measure the lesion size (in three dimensions), and assign the region of interest (ROI) for PET imaging analysis.

Quantitative analysis of  $^{18}\text{F}$ -FES uptake will be performed at the lesion-level. Standardized uptake values (SUV) will be measured by manually drawing a region of interest (ROI) to encompass the entire lesion guided by the lesion extent visualized on MRI. For the primary objective, the maximum SUV value (SUVmax) will be determined. For potential exploratory analyses, additional uptake values may include SUVpeak (small fixed-size ROI centered on most intense part of tumor), SUVmean (average value), SUVmin (minimum value), SUVsd (standard deviation), tumor-to-normal tissue uptake ratios, FTV (functional tumor volume; i.e. the volume of tumor tissue with increased  $^{18}\text{F}$ -FES uptake) and TLU (total lesion uptake; i.e. the product of FTV  $\times$  SUVmean). A research workstation/software (e.g. Mirada Medical) will be used to perform these advanced quantitative techniques.

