## STUDY DESIGN

This is a prospective, one-arm, observational study which will enroll patients with biopsy-proven DCIS scheduled for diagnostic breast MRI for preoperative staging/extent of disease evaluation as part of standard of care. Eligible patients will be consented for participation in the research study which includes a directed breast PET/MRI with F-FES. F-FES uptake of the known malignancy will be measured on the PET/MRI examination using standardized uptake values (SUV) and tumor-to-normal tissue ratios. The proposed work-flow is described in the schema.

---

[figure not shown]
\* Patients with newly diagnosed DCIS from a screening breast MRI are also eligible to participate in this study. For these subjects, the research breast PET/MRI should be performed prior to any treatment or surgery for DCIS.

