## 12. STATISTICAL CONSIDERATIONS

### 12.1 Primary Objective

*To compare quantitative  $^{18}\text{F}$ -FES uptake of biopsy-proven DCIS measured using PET/MRI with ER protein levels determined by immunohistochemistry.*

The primary objective is to compare  $^{18}\text{F}$ -FES  $\text{SUV}_{\max}$  from PET/MRI with the ER immunohistochemistry semi-quantitative score obtained by using the Allred score. We will test the hypothesis that  $^{18}\text{F}$ -FES  $\text{SUV}_{\max}$  from PET/MRI correlates well against the ER IHC Allred score. The correlation of the two measures will be evaluated using Spearman correlation. The null hypothesis is  $H_0: p_0=0.00$  and the alternative hypothesis is  $H_1: p_1=0.73$ .

A sample size of 12 patients achieves 82% power ( $\beta=0.20$ ) for detecting an expected correlation coefficient ( $r=0.73$ ) to be significantly different from zero with two-tailed  $\alpha$  value of 0.05 (<http://www.sample-size.net/correlation-sample-size/>). We anticipate enrolling 1 subject every 1-2 months. The number of subjects with ER-negative DCIS will be limited to  $\leq 3$ .

Other measures of  $^{18}\text{F}$ -FES uptake including  $\text{SUV}_{\text{peak}}$ ,  $\text{SUV}_{\text{mean}}$ , tumor-to-normal tissue uptake ratio, and total lesion uptake will also be correlated with the ER immunohistochemistry semi-quantitative score obtained by using the Allred score.

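### Does measuring FES uptake per lesion mean that patients with several lesions are counted more than once in the 12-patient primary test?

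*Combined protocol and SAP*

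**What the plan says.** Section 5.5.6 (image analysis) opens with lesion identification: "The known biopsy-proven breast cancer(s) will be identified on the MRI/PET examination". It then states that quantitative analysis of FES "uptake will be performed at the lesion-level", explains that the region of interest is drawn by hand around the whole lesion as seen on MRI, and names SUVmax as the measure for the primary objective.

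Section 12.1 counts patients: "A sample size of 12 patients achieves 82% power" for an expected correlation of 0.73 to be "significantly different from zero with two-tailed" alpha of 0.05. On the method it says "The correlation of the two measures will be evaluated using Spearman correlation". It gives no index-lesion rule, no per-patient summary and no allowance for clustering.

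The Study Design paragraph of the protocol summary uses the singular: "uptake of the known malignancy will be measured on the PET/MRI examination". Section 5.4 foresees the "identification of unsuspected suspicious findings requiring biopsy" on the clinical MRI and allows the research scan to follow such a biopsy.

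**The concern.** Two units appear, the lesion in Section 5.5.6 and the patient in Section 12.1, and no sentence connects them. More than one lesion per patient is possible. Section 4.1 does not exclude multifocal or bilateral disease, Section 5.5.6 uses optional plurals, and a biopsy prompted by the clinical MRI can come before the research scan.

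Lesions in one woman share hormone levels, tracer dose, scanner calibration and probably receptor biology. If each lesion entered the Spearman test as a separate observation, the nominal sample size would exceed the number of independent units and the p-value would be too small. The ROC analysis for ER status would be especially exposed, because Section 12.1 allows at most 3 ER-negative subjects.

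**Working it through.** **1. The plan's own figure.** Inputs from Section 12.1: n = 12, r = 0.73, null value 0, two-sided alpha 0.05.

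- Fisher transform: atanh(0.73) = 0.929.
- Sample size for 80% power: ((1.960 + 0.842)/0.929)² + 3 = 12.1, against 12 in the plan.
- Power at n = 12, plain Fisher z: Φ(0.929 × √9 − 1.960) = Φ(0.826) = 79.6%.
- With the small-sample term r/(2(n − 1)) = 0.73/22 = 0.033: Φ((0.929 + 0.033) × 3 − 1.960) = Φ(0.926) = 82.3%, against 82% in the plan.

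The stated 82% is reproduced with 12 independent observations, and the plan calls those 12 observations patients. (This formula is for a Pearson-type correlation. How well it serves a Spearman test is a separate matter.)

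**2. Which unit does the text use, and where?**

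| Place | What is counted or described | Unit |
|---|---|---|
| Number of Subjects; 12.1 | Sample size | Patient |
| 12.1 | Cap on ER-negative cases | Subject |
| 12.2, item 2 | Test-retest set, up to 5 | Subject |
| 12.2, item 5 | Upgrade rate, numerator and denominator | Patient |
| Study Design (summary) | The malignancy measured | One per patient, implied by the singular |
| 13.2 | Slides for Allred re-scoring, if the report is insufficient | The biopsy that made the first diagnosis |
| 5.5.6 | How uptake is extracted from the image | Lesion |

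The lesion appears as the unit only where SUV is being measured. SUVmax is a property of a region of interest, so lesion-level is the ordinary description of that step. Nowhere is a second lesion's Allred score provided for, and nowhere are several lesions from one patient said to enter a test as separate pairs.

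**3. What if all lesions were pooled anyway?** The documents give neither the number of multi-lesion patients nor the within-patient correlation, so both are assumed. In the simulation SUVmax and Allred are unrelated, each has the same within-patient correlation w, and the Spearman test uses the t approximation. There are 30,000 runs per cell, with a Monte Carlo standard error of about 0.13 to 0.25 points. Rejection rate at nominal 5%:

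| 12 patients, of whom | Pairs | w = 0.3 | w = 0.5 | w = 0.7 | w = 0.8 |
|---|---|---|---|---|---|
| none has a second lesion | 12 | 5.2% | 5.0% | 5.3% | 5.2% |
| 1 has two lesions | 13 | 5.4% | 5.9% | 6.0% | 6.3% |
| 3 have two lesions | 15 | 5.6% | 6.1% | 7.0% | 7.9% |
| 6 have two lesions | 18 | 5.9% | 6.6% | 8.8% | 9.9% |
| all 12 have two lesions | 24 | 5.9% | 7.8% | 10.6% | 12.4% |

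A tied, Allred-like scale at w = 0.7 gives 6.9% with 15 pairs and 10.0% with 24, so ties do not alter the picture. The first row is the one-pair-per-patient reading. It is nominal apart from the small excess of the t approximation at n = 12.

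**4. What inflation requires.** Three things must hold together: some patients have more than one proven DCIS lesion, all those lesions are entered as independent, and both SUVmax and Allred are correlated within patient. The second would be the analyst's own decision, and the plan does not ask for it.

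**The case for a change.** The best counter-argument is that the lesion-level statement and the primary SUVmax definition stand in the same paragraph, so the statement governs the primary variable. Reading it as only one region of interest per lesion then leaves someone to choose which lesion represents a two-lesion patient. In the extreme case, picking the lesion that gives the smallest p-value, the simulated false-positive rate is about 8% to 9% with two such patients and 12% to 15% with four (within-patient correlation 0.8 and 0.6). The hormone analyses raise the same question, because Section 5.6 takes one blood sample per scan. Pooling two SUVmax values against one hormone value gives 7.2% to 7.8% with two such patients and 8.5% to 10.0% with four (correlation 0.6 and 0.8).

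The gap itself stands: no sentence names the index lesion. The consequences do not follow from the plan. The smallest-p-value figures describe deliberate selection on the result, which no plan endorses. A choice made without looking at how SUVmax pairs with Allred leaves 12 independent pairs and a nominal level. Section 13.2 also points to a natural choice, the lesion of the first diagnostic biopsy, although it covers only cases where the report lacks the scoring data. Sections 5.4 and 5.5.1 prefer the research scan before any MRI-prompted biopsy. In the main design of Section 5.1 PET is acquired during the clinical MRI, so findings from that MRI are not yet biopsied at the scan.

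A related worry is that a further lesion could be invasive and still enter the analysis. The primary objective is confined to biopsy-proven DCIS, and Section 4.1 requires no invasion or microinvasion. The generic term breast cancer in Section 5.5.6 does not widen that.

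**Conclusion.** The concern does not call for a change. The plan measures uptake per lesion and tests by patient. These are compatible, and the missing link is which lesion stands for a patient with more than one. An analyst following Section 12 would use one pair per patient. That keeps n at 12, leaves the reproduced 82% power calculation as it is, and holds the type I error at 5.0% to 5.3%.

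If all lesions were pooled, the excess would be modest with few multi-lesion patients: 5.4% to 6.3% with one, 5.6% to 7.9% with three. It approaches or exceeds 10% only if half or more of the patients had a second proven lesion and the within-patient correlation were high. These figures rest on assumed lesion counts and on correlations of 0.3 to 0.8 in both measures. Writing the lesion choice down would record the sensible reading and would not alter the result obtained under it.

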### 13. PATHOLOGY REVIEW

#### 13.1 Justification

The pathology of the biopsy-proven breast cancer will be evaluated per the current standard of care (histologic diagnosis, grade, tumor biomarker status). ER status is reported as positive or negative and includes a percentage of cells staining positive as well as intensity of staining. This information will be obtained from the clinical pathology report in the subjects' electronic medical record and will be used to calculate a semi-quantitative Allred score (44). If the information needed to calculate the Allred score is not included in the clinical pathology report, a pathologist on the research study team will review the existing ER IHC slides. If the information needed to determine tumor cell density is not included in the clinical pathology report, a pathologist on the research study team will review the existing H&E slides.

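### The plan does not mask the person who draws the PET regions of interest to ER status, which the team collects before the scan; this leaves the primary correlation open to upward bias.

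*Combined protocol and SAP*

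**What the plan says.** **Index measure.** Section 5.5.6 obtains SUV by "manually drawing a region of interest (ROI) to encompass the entire lesion", "guided by the lesion extent visualized on MRI". It continues: "For the primary objective, the maximum SUV value" is used. It gives no reader, number of readers, masking rule or lock of values. Section 12.1 also correlates SUVmean and total lesion uptake, among other measures, with Allred.

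**Reference standard.** Section 5.2 computes Allred from percentage and intensity of staining: "This information will be obtained from the clinical pathology report". Only if the report lacks the information does Section 13.1 provide that "a pathologist on the research study team will review the existing ER IHC slides". The same section lets a study pathologist determine tumor cell density from H&E slides when the report does not give it. Neither provision mentions the SUV results.

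**When ER status is known.** Table 2 lists biopsy pathology reports at Baseline, and its note (d) records "standard clinical histopathology including tumor biomarkers". Note (a) reads "Baseline is defined as the time period from initial subject contact until injection of" the tracer.

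**How ER status is used.** Section 12.1: "The number of subjects with ER-negative DCIS will be limited to" at most 3. Section 5.8 counts up to 5 ER+ patients for the retest scan. Under Section 6.1 breast imaging radiologists may determine eligibility, and the radiologist who checks radiologic-pathologic concordance after biopsy may flag patients.

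**The concern.** The primary result compares a reader-dependent measurement with a reference value that the team holds before the image is read. The stated hypothesis is a positive correlation. A reader who knows that a lesion is ER-negative may, without intending to, draw tighter or choose a fainter focus, and may be more generous with an ER+ lesion. Both habits push SUVmax and Allred into agreement.

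The design gives a few lesions much weight. With 12 patients and at most 3 ER-negative, each ER-negative lesion carries at least one third of the specificity behind the ER+/ER-negative cut-point (Section 12.2, item 1). The same lesions hold the lowest Allred ranks in the Spearman coefficient. ER-dependent contouring of those few could raise the primary correlation and the AUC, move the cut-point, and flatter the sensitivity and specificity reported at it.

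**Working it through.** **1. The plan's own figure.** Section 12.1 gives 82% power for r = 0.73 against 0, with n = 12 and two-sided α = 0.05.

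- Plain Fisher z: atanh(0.73) × √(12 − 3) − 1.960 = 0.929 × 3 − 1.960 = 0.826, so power is 79.6%.
- With the small-sample term r/(2(n − 1)) = 0.73/22 = 0.033 and the t-based critical value r = 2.228/√(10 + 2.228²) = 0.576 (atanh = 0.656): (0.929 + 0.033 − 0.656) × 3 ≈ 0.916, so power is 82.0%.

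The stated figure reproduces, and masking changes neither it nor the 12 patients. Precision is low in any case: the approximate 95% interval around r = 0.73 is tanh(0.929 ± 1.96/3), or 0.27 to 0.92.

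**2. Does any section close the gap?**

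- Sections 5.1 and 7 keep PET results out of patient management and the medical record. That shields the clinicians, not the research reader.
- Section 5.5.5 refers to a separate Imaging Manual, described as covering acquisition and reconstruction. Reading is not mentioned. The manual itself was not available.
- Section 14.3 assigns study numbers for confidentiality. It does not say that ER status is withheld from the reader.

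**3. Illustration of size.** These assumptions are not in the documents: Allred values 0, 0, 0, 5, 6, 6, 7, 7, 8, 8, 8, 8; normal SUVmax; ER-negative lesions read lower than ER+ lesions by d SD; Spearman test by the t approximation at two-sided 5%; 20,000 runs. Ranks depend only on differences, so lowering the three ER-negative lesions by d is the same as raising all nine ER+ lesions by d. The AUC column, for no true association, is Φ(d/√2).

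| d (SD) | Mean rho, no true association | False-positive rate | AUC | Mean rho, latent r = 0.50 | Rejection rate, latent r = 0.50 |
|---|---|---|---|---|---|
| 0 | 0.00 | 5.1% | 0.50 | 0.43 | 31% |
| 0.25 | 0.08 | 5.8% | 0.57 | 0.49 | 41% |
| 0.5 | 0.16 | 8.3% | 0.64 | 0.55 | 50% |
| 1.0 | 0.30 | 15.5% | 0.76 | 0.63 | 65% |

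A repeat of the no-association case with 400,000 runs gave 5.3%, 5.9%, 7.9% and 15.4%. In that repeat, lowering only one of the three ER-negative lesions by 1 SD gave 5.7%, and lowering two gave 8.8%.

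**The case against.** **The reader may be masked in practice.** No section names the person who draws the ROIs. A reader might infer from the accrual cap and the screening route that this person knows each patient's ER status. The documents show only that someone on the team must know it; that this is the ROI reader is an inference. This objection stands, and the point is therefore that masking is not required.

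**MRI sets the boundary.** The ROI is guided by MRI extent and covers the whole lesion, and SUVmax is a single voxel. Moving a boundary through cold tissue changes nothing, so it would be too strong to say that the reader freely decides whether a hot voxel counts. This stands in part. Judgment remains over lesion extent, which focus is the lesion, and whether adjacent uptake falls inside. SUVmean and total lesion uptake depend more on the contour. Section 5.5.6 calls them potential exploratory values, but Section 12.1 says they will be correlated with Allred.

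**The reference side is better protected.** Allred normally comes from the clinical report, on biopsy tissue, and PET results do not enter the record. Study scoring is a fallback, and cell density is exploratory. This stands, so the pathology half is the lesser part.

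**The simulated shifts are assumed.** At 0.25 SD the rise is under one percentage point, and 15% needs all three ER-negative lesions to read a full SD low. This also stands. It does not require every lesion to be misread, since three are enough.

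**Conclusion.** The point holds as a risk of bias that the plan leaves open. Documented: a manual index measure, ER status held by the team before the scan and used to run accrual, and no masking of the ROI reader or of a study pathologist. Inferred: that the ROI reader will know ER status. The likely direction is upward for the primary correlation and the ER+/ER-negative AUC. The direction in which the cut-point would move depends on which lesions are affected.

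The false-positive rates of about 6%, 8% and 15% for shifts of 0.25, 0.5 and 1 SD rest wholly on the assumed shift and Allred mix; the documents give no basis for choosing among them. A reader might conclude that the correlation will be inflated, or that the sample size is wrong. Neither follows: no bias has been shown, and the 12 patients and 82% power are not altered by this point.

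The change is worth making because it is cheap and must come first: once a reader has contoured with knowledge of ER status, that reading cannot be made masked afterwards.

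**What to change.** **Section 5.5.6.** State that ROIs are drawn on coded images by an existing team member who did not screen the patient. Supply the lesion location but withhold ER status, Allred score and the pathology report. Lock the SUV values before they are linked to ER data. Code the up to 5 retest scans as separate examinations, because a second scan marks a patient as ER+.

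**Section 13.1.** State that when a study pathologist scores Allred or tumor cell density, this is done without the SUV results.

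**Cost.** A short addition to each section and the coding of 12 scans, or up to 17 with retests (12 + 5). The screening investigator should not be the ROI reader. No additional patients, scans or staff are needed.
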